3.1.3. Exploratory Efficacy Endpoints

3.1.3.1. Exploratory Efficacy Endpoints Evaluated At Month 3

- MGYLS
 - Proportion of patients with MGYLS >2 at Day 14, Month 1.5, and Month 3.
- Meibomian Glands Yielding Optimal Liquid Secretion (MGYOLS, e.g., number of expressible glands yielding clear meibum)
 - Change from Baseline at Day 14, Month 1.5, and Month 3 in MGYOLS.
 - Proportion of patients with MGYOLS score >2 at Day 14, Month 1.5, and Month 3.
- OSDI total score and subscales
 - Proportion of patients with OSDI total score Decrease from Baseline >4.5 at Month 3 (4.5 is the minimally important clinical difference for early to moderate disease).
 - Change from Baseline at Day 14, Month 1.5, and Month 3 in OSDI subscales
- SPEED
 - Proportion of patients with SPEED <6 at Day 14, Month 1.5, and Month 3
- TBUT
 - Change from Baseline at Day 14, Month 1.5, and Month 3 in TBUT.
 - Proportion of patients with TBUT score >5 at Day 14, Month 1.5, and Month 3.
 - Proportion of patients with TBUT score >10 at Day 14, Month 1.5, and Month 3.
- Schirmer's Test without Anesthesia
 - Change from Baseline at Day 14, Month 1.5, and Month 3 in Schirmer's test.
 - Proportion of patients with Schirmer's test result ≥ 10 mm at Day 14, Month 1.5, and Month 3.
- VAS
 - Change from Baseline at Day 14, Month 1.5, and Month 3 in individual VAS results (besides eye dryness), Average VAS, and Worst VAS, separately.
 - Proportion of patients with score decreased by ≥ 5 , separately for Average VAS and Worst VAS, at Day 14, Month 1.5, and Month 3.
- Other
 - Eyelid margin erythema/telangiectasias at Day 14, Month 1.5, and Month 3.
 - Corneal and conjunctival staining (0 to 5 scale) at Day 14, Month 1.5, and Month 3.

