3.1.3.2. Exploratory Efficacy Endpoints Evaluated After Completion of Safety Follow-up Period

- MGYLS
 - Change from Baseline at Month 4.5 and Month 6 in MGYLS.
 - Proportion of patients with a change from baseline in MGYLS score ≥ 5 at Month 4.5 and Month 6.
 - Proportion of patients with MGYLS > 2 at Month 4.5 and Month 6.

- OSDI total score and subscales
 - Change from Baseline at Month 4.5 and Month 6 in OSDI total score
 - Proportion of patients with OSDI total score < 13 at Month 4.5 and Month 6
 - Proportion of patients with OSDI total score Decrease from Baseline >4.5 at Month 6.
 - Change from Baseline at Month 4.5 and Month 6 in OSDI subscales.
- SPEED
 - Change from Baseline at Month 4.5 and Month 6 in SPEED
 - Proportion of patients with SPEED <6 at Month 4.5 and Month 6
- VAS
 - Change from Baseline at Month 4.5 and Month 6 in individual VAS results, Average VAS, and Worst VAS, separately.
 - Proportion of patients with score decreased by ≥ 5 , separately for Average VAS and Worst VAS, at Month 4.5 and Month 6.
- MGS
 - Change from Baseline at Month 4.5 and Month 6 in MGS.
 - Proportion of patients with MGS score >12 at Month 4.5 and Month 6.
- MGYOLS
 - Change from Baseline at Month 4.5 and Month 6 in MGYOLS.
 - Proportion of patients with MGYOLS score >2 at Month 4.5 and Month 6.
- TBUT
 - Change from Baseline at Month 4.5 and Month 6 in TBUT.
 - Proportion of patients with TBUT score >5 at Month 4.5 and Month 6.
 - Proportion of patients with TBUT score >10 at Month 4.5 and Month 6.
- Schirmer's Test without Anesthesia
 - Change from Baseline at Month 4.5 and Month 6 in Schirmer's test.
 - Proportion of patients with Schirmer's test result ≥ 10 mm at Month 4.5 and Month 6.
- Other
 - Eyelid margin erythema/telangiectasias at Month 4.5 and Month 6.
 - Corneal and conjunctival staining (0 to 5 scale) at Month 4.5 and Month 6.

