For assessments not scheduled at every study visit: The same approach will be used, omitting the visits without planned assessments from the algorithm. For example, vital signs and Schirmer's assessment are planned for Baseline, Month 3, and Month 6 visits. The numbers of days between those visits are 83 in both cases, resulting in the first 41 days of the period being assigned to the earlier visit. Therefore:

- Baseline visit date through the Baseline visit date + 41 would be assigned to the Baseline visit;
- Baseline visit date + 42 through Baseline visit date + 125 would be assigned to the Month 3 visit, and
- Baseline visit date + 126 or later to the Month 3 visit.

In cases where an assessment is not scheduled to be performed at the Baseline visit, but is scheduled only at the Screening visit, Month 3, and Month 6, (such as IOP, meibography, or ophthalmology), visits prior to and including the Baseline visit will be windowed to the Screening visit, and visits between the Baseline and Month 3 visits will be windowed to Month 3. Visits between Month 3 and Month 6 will be split as described above.

Assessments conducted at the time of **early termination** (defined as assessments performed on the date of early termination or recorded on the same date as an End of Study visit is entered in the subject visit case report form [CRF] page) will also be mapped to the nearest planned visit, as described for unscheduled visits.

Table 3 Mapping of Unscheduled and Early Termination Visits

Visit	Date with Regards to Baseline Visit	Study Day	Analysis Visit Mapping		
			Assessments Performed Each Visit	Assessments Performed at Screening, Baseline, Month 3, and Month 6	Assessments Performed at Screening, Month 3, and Month 6
Screening	Baseline -14 d	-14	Screening	Screening	Screening
Baseline	Baseline	1	Baseline	Baseline	
			
	Baseline + 6 d	7			
	Baseline + 7 d	8			
			
Day 14	Baseline + 14 d	15	Day 14		Month 3

Visit	Date with Regards to Baseline Visit	Study Day	Analysis Visit Mapping		
			Assessments Performed Each Visit	Assessments Performed at Screening, Baseline, Month 3, and Month 6	Assessments Performed at Screening, Month 3, and Month 6
			
	Baseline + 26 d	27			
	Baseline + 27 d	28	Month 1.5		
			
	Baseline + 41 d	42			
Month 1.5	Baseline + 42 d	43			
	Month 3	Month 3	
	Baseline+61 d	62			
	Baseline+62 d	63			
			
Month 3	Baseline + 84 d	85	Month 4.5		
			
	Baseline+103 d	104			
	Baseline+104 d	105			
	Month 6	Month 6	Month 6
	Baseline+125 d	126			

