Change from baseline in Average VAS and Worst VAS at Day 14, Month 1.5 and Month 3 will be analyzed as described for MGYLS in [Section 8.1.1](#).

Proportion of Average VAS responders based on decrease ≥ 5 and proportion of Worst VAS responders based on decrease ≥ 5 will be analyzed through Month 3 as described for the proportion of MGYLS responders, using a CMH test (or chi-square/Fisher's Exact if CMH is not estimable) to evaluate the difference between treatments, controlling for duration of disease category and baseline MGS score category.

Change from Schirmer's assessment at Day 14, Month 1.5 and Month 3 will be analyzed as described for MGYLS in [Section 8.1.1](#).

Proportion of Schirmer's ≥ 10 mm responders will be analyzed through Month 3 as described for the proportion of MGYLS responders, using a CMH test (or chi-square/Fisher's Exact if CMH is not estimable) to evaluate the difference between treatments, controlling for duration of disease category and baseline MGS score category.

Change from baseline in Burning/Stinging VAS, Itching VAS, Foreign Body Sensation VAS, Eye Discomfort VAS, Photophobia VAS, and Pain VAS at Day 14, Month 1.5 and Month 3 will be analyzed as described for MGYLS in [Section 8.1.1](#).

Proportion of patients with clinical cure, defined as having MGYLS change from baseline ≥ 5 and OSDI total score < 13 , will be analyzed through Month 3 as described for the proportion of MGYLS responders, using a CMH test (or chi-square/Fisher's Exact if CMH is not estimable) to evaluate the difference between treatments, controlling for duration of disease category and baseline MGS score category.

Eyelid margin erythema and telangiectasias results will be summarized by time point, in conjunction with other findings from the slit lamp examination. Actual values and shifts from baseline through Month 3 will be summarized by parameter and time point. Changes from baseline will be analyzed at each time point using CMH statistics to evaluate the differences between each AZR-MD-001 treatment group and placebo, controlling for baseline value, using the following pseudocode:

```
PROC FREQ data=xxx;
  BY visit;
  TABLE treatment * base * result / CMH;
  ODS output CMH=outcmh (where=(ALTHYPOTHESIS='General Association'));
run;
```

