Proportion of Average VAS responders based on decrease ≥ 5 and proportion of Worst VAS responders based on decrease ≥ 5 at Month 4.5 and Month 6 will be analyzed as described for the proportion of MGYLS responders, using a CMH test (or chi-square/Fisher's Exact if CMH is not estimable) to evaluate the difference between treatments, controlling for duration of disease category and baseline MGS score category.

Change from Schirmer's assessment at Month 4.5 and Month 6 will be analyzed as described for MGYLS in [Section 8.1.1](#).

Proportion of Schirmer's ≥ 10 mm responders at Month 4.5 and Month 6 will be analyzed as described for the proportion of MGYLS responders, using a CMH test (or chi-square/Fisher's Exact if CMH is not estimable), as described in [Section 8.3.1](#).

Proportion of patients with clinical cure, defined as having MGYLS change from baseline ≥ 5 and OSDI total score < 13 , will be analyzed at Month 4.5 and Month 6 as described for the proportion of MGYLS responders, using a CMH test (or chi-square/Fisher's Exact if CMH is not estimable), as described in [Section 8.3.1](#).

Eyelid margin erythema and telangiectasias changes from baseline will be analyzed at Month 4.5 and Month 6, using CMH statistics as described in [Section 8.3.1](#).

Corneal and conjunctival staining shifts from baseline will be analyzed using CMH statistics, as described in [Section 8.3.1](#).

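### The SAP analyses Schirmer results at three visits where the test is not scheduled, and one line of its visit-window text labels late unscheduled and early-exit values Month 3 instead of Month 6

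*SAP*

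**What the plan says.** **Schedule.** SAP Table 2 (section 2.6) marks the Schirmer test at Screening, Baseline, Month 3 and Month 6. Protocol Table 1 (section 1.3) agrees for the Expansion Cohort; its additional Month 1 test belongs to a visit for Cohort 1 only. SAP 5.1 repeats that "vital signs and Schirmer's assessment are planned for Baseline, Month 3, and Month 6 visits".

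**Endpoints.** SAP 3.1.3.1 lists "Change from Baseline at Day 14, Month 1.5, and Month 3 in Schirmer's test" and a responder endpoint (result of at least 10 mm) "at Day 14, Month 1.5, and Month 3". SAP 3.1.3.2 adds "Change from Baseline at Month 4.5 and Month 6 in Schirmer's test" and the responder endpoint at those two visits.

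**Analyses.** SAP 8.3.1 states "Change from Schirmer's assessment at Day 14, Month 1.5 and Month 3 will be analyzed" by the method used for MGYLS. It analyses the responders by CMH test through Month 3, without naming the visits. SAP 8.3.2 states "Change from Schirmer's assessment at Month 4.5 and Month 6 will be analyzed" and names the same two visits for responders.

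**Windows.** For assessments not made at every visit, SAP 5.1 splits each interval between planned visits and ends the Month 3 window at Baseline + 125 days. Its last bullet then reads "Baseline visit date + 126 or later to the Month 3 visit". Table 3 ends with a Month 6 band for these assessments. The mapping covers unscheduled and early-termination assessments. When several values fall in one analysis visit, the chronologically later one is used.

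**The concern.** An endpoint list that names visits without a measurement cannot be executed as written. The programmer must leave cells empty, drop the visits without a documented decision, or let an imputation model fill them. The last would produce estimates and p-values at Day 14, Month 1.5 and Month 4.5 with no Schirmer reading behind them, and nothing in the table would tell the reader so.

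The window bullet raises a different problem. Protocol 1.2 asks Expansion Cohort patients who leave early to complete the Month 6 procedures, which include Schirmer and vital signs. An exit late in follow-up therefore yields values that the mapping must place. If the bullet is followed, those values go to the wrong visit, and the later-value rule lets them displace a correctly timed Month 3 reading.

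**Working it through.** **Part 1: visits analysed against visits measured**

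Visit days are from SAP 5.1, the schedule from SAP Table 2, and the analysed visits from SAP 3.1.3 and 8.3.

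| Visit | Days after Baseline | Schirmer scheduled | Schirmer analysed |
|---|---|---|---|
| Day 14 | 14 | no | yes |
| Month 1.5 | 42 | no | yes |
| Month 3 | 84 | yes | yes |
| Month 4.5 | 126 | no | yes |
| Month 6 | 168 | yes | yes |

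There are two endpoints (change; at least 10 mm), and each of two doses is compared with placebo.

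- Planned comparisons: 5 visits × 2 endpoints × 2 doses = 20.
- At visits with no scheduled test: 3 × 2 × 2 = 12.
- With scheduled data: 2 × 2 × 2 = 8.

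The count takes the responder visits from the endpoint list in 3.1.3.1, because 8.3.1 does not name them. If the responder test in 8.3.1 were read as Month 3 only, the change endpoint would give 5 × 2 = 10 comparisons and the responder endpoint 3 × 2 = 6, a total of 16. Those without data would be 3 × 2 + 1 × 2 = 8. On either reading at least half have no data.

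Unscheduled tests cannot fill the gap. The SAP 5.1 rule creates only Baseline, Month 3 and Month 6 windows for Schirmer, so no value can be filed at Day 14, Month 1.5 or Month 4.5.

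**Part 2: the window rule**

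The SAP rule is: gap = days strictly between two planned visits; the first half, rounded down, goes to the earlier visit; the next window starts the following day. Schirmer and vital signs are planned at days 0, 84 and 168.

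- Baseline to Month 3: 84 − 0 − 1 = 83; 83 / 2 rounded down = 41. Baseline window: 0 to +41.
- Month 3 to Month 6: 168 − 84 − 1 = 83; again 41. Month 3 window: +42 to 84 + 41 = +125.
- Remainder: +126 onward, which is Month 6.

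The SAP's cut-offs of 41, 42, 125 and 126 all reproduce. Only the label on the last window does not. Day +126 itself is equidistant (126 − 84 = 42; 168 − 126 = 42), so the split rule decides it; every later day is nearer to Month 6.

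As an illustration, take a patient tested at Month 3 on day +84 who leaves on day +126 and has the exit procedures done.

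| Rule followed | Month 3 value in Month 6 outputs | Month 6 value |
|---|---|---|
| Split rule and Table 3 | day +84 | day +126 |
| Last bullet of 5.1 | day +126 (later value wins) | none |

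Appendix 5 of the SAP says the end-of-follow-up tables carry the earlier period as well, so the displaced Month 3 value would appear there. The Month 3 tables are protected because SAP 14 restricts them to information collected through Month 3.

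**The case against.** The strongest reply is that neither fault can do much harm.

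**On imputation.** No Schirmer imputation model is written. The model in SAP 5.3.1.1 is for the primary analysis and names MGYLS and OSDI total score. SAP 8.2 says expressly that imputation applies, the opening of 8.3 does not, and 8.3.2 mentions it only for MGYLS and OSDI. SAP 14.2.4.2 already provides a code for p-values that cannot be estimated. This stands in part. Against it, SAP 5.3 extends imputation to most other efficacy analyses, 5.3.1.2 speaks of each assessment, and 8.3.1 sends Schirmer change to the method of 8.1.1, which uses imputation. Imputing Schirmer is therefore plausible but not settled, and the conclusion must be conditional. A reader might infer that wholly empty visit columns would also block or distort the legitimate Month 3 and Month 6 imputation. The documents do not show that.

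**On the window bullet.** The preceding bullet, the split rule and Table 3 all point to Month 6, so this is most likely a slip that a careful programmer would catch. That also stands. A reader might infer that all late Schirmer values, including the scheduled Month 6 test, are misfiled, or that every patient with a late value is affected. The rule covers unscheduled and early-termination values only, and if Table 3 is followed nobody is affected.

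**On importance.** The Schirmer endpoints are exploratory and outside the testing hierarchy in 8.1.1. SAP 8 makes p-values at Month 4.5 and Month 6 descriptive. Vital signs are only summarised as absolute values (10.6). All of this stands and limits the severity.

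What the reply does not remove is the contradiction. SAP 12 does not explain the extra visits. Protocol 9.4.3 lists the 10 mm criterion at every visit, which may be where they came from, but the protocol's own schedule does not support it.

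**Conclusion.** Both inconsistencies are confirmed from the documents. Twelve of the 20 planned exploratory Schirmer comparisons fall at visits with no scheduled test. They would be not estimable or, if the visit-wise imputation is applied, wholly model-generated. The last window bullet in SAP 5.1 contradicts the SAP's own rule and Table 3. Taken literally, in the Month 6 outputs it would remove late unscheduled and early-termination Schirmer and vital-sign values from Month 6 and could overwrite true Month 3 values. The documents give no rate of such visits, so the number of patients cannot be stated.

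Month 3 outputs, the primary endpoints and type I error control are unaffected. MGYLS and OSDI are collected at every visit and use a different window list. The statement about Month 3 outputs assumes that the provision in SAP 14 for early-termination visits of patients without a Month 3 visit is bounded by the same Month 3 data limit.

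This is a minor consistency correction to exploratory and descriptive outputs.

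**What to change.** - In SAP 3.1.3.1 and 8.3.1, restrict Schirmer change and the 10 mm responder endpoint to Month 3, naming the visit for responders. In 3.1.3.2 and 8.3.2, restrict both to Month 6.
- State whether Schirmer is multiply imputed. If it is, include only the visits at which it is measured (Baseline, Month 3 and, for the later analysis, Month 6).
- In the last bullet of the SAP 5.1 list for assessments not made at every visit, replace Month 3 with Month 6, so that text and Table 3 agree.

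The cost is SAP wording and, where they show the extra visits, the table shells. No procedure, data collection or sample size changes. It is best done before the Month 3 database freeze, so that the choice is documented before anyone is unmasked.

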3.1.3.2. Exploratory Efficacy Endpoints Evaluated After Completion of Safety Follow-up Period

- MGYLS
 - Change from Baseline at Month 4.5 and Month 6 in MGYLS.
 - Proportion of patients with a change from baseline in MGYLS score ≥ 5 at Month 4.5 and Month 6.
 - Proportion of patients with MGYLS > 2 at Month 4.5 and Month 6.

- OSDI total score and subscales
 - Change from Baseline at Month 4.5 and Month 6 in OSDI total score
 - Proportion of patients with OSDI total score < 13 at Month 4.5 and Month 6
 - Proportion of patients with OSDI total score Decrease from Baseline >4.5 at Month 6.
 - Change from Baseline at Month 4.5 and Month 6 in OSDI subscales.
- SPEED
 - Change from Baseline at Month 4.5 and Month 6 in SPEED
 - Proportion of patients with SPEED <6 at Month 4.5 and Month 6
- VAS
 - Change from Baseline at Month 4.5 and Month 6 in individual VAS results, Average VAS, and Worst VAS, separately.
 - Proportion of patients with score decreased by ≥ 5 , separately for Average VAS and Worst VAS, at Month 4.5 and Month 6.
- MGS
 - Change from Baseline at Month 4.5 and Month 6 in MGS.
 - Proportion of patients with MGS score >12 at Month 4.5 and Month 6.
- MGYOLS
 - Change from Baseline at Month 4.5 and Month 6 in MGYOLS.
 - Proportion of patients with MGYOLS score >2 at Month 4.5 and Month 6.
- TBUT
 - Change from Baseline at Month 4.5 and Month 6 in TBUT.
 - Proportion of patients with TBUT score >5 at Month 4.5 and Month 6.
 - Proportion of patients with TBUT score >10 at Month 4.5 and Month 6.
- Schirmer's Test without Anesthesia
 - Change from Baseline at Month 4.5 and Month 6 in Schirmer's test.
 - Proportion of patients with Schirmer's test result ≥ 10 mm at Month 4.5 and Month 6.
- Other
 - Eyelid margin erythema/telangiectasias at Month 4.5 and Month 6.
 - Corneal and conjunctival staining (0 to 5 scale) at Month 4.5 and Month 6.

3.2. Safety Endpoints

Safety endpoints will be evaluated through Month 3, and supplemental safety analyses (including information collected through Month 6) will be evaluated at the end of the safety follow-up period. Safety endpoints include:

- Adverse events
- Vital signs
- BCVA (Logarithmic visual acuity chart)
- Biomicroscopy (Slit Lamp)

- Ophthalmoscopy
- Intraocular pressure (IOP)
- Conjunctival hyperemia (redness)

4. ANALYSIS SETS

4.1. Intent-to-Treat Analysis Set

The Intent-to-Treat (ITT) Set will include all patients who were randomized. Patients will be analyzed according to treatment as randomized. The ITT Set will be used for analyses of efficacy data.

4.2. Modified Intent-to-Treat Analysis Set

The Modified Intent-to-Treat (mITT) Set will be comprised of all randomized patients who meet inclusion/exclusion criteria, have MGS values at randomization, have baseline OSDI <34, and received 1 or more applications of randomized study treatment. All patients in the mITT Set will be analyzed by the treatment as randomized. This population will be used for primary efficacy analyses.

4.3. Per-Protocol Analysis Set, Month 3

The Per-Protocol (PP) Set will be comprised of all mITT patients who do not have a Grade 4 or Grade 5 protocol deviation impacting Baseline through Month 3 (as per [Section 7](#)). Deviations which end before the Baseline visit date or begin after the Month 3 visit will not impact inclusion in the PP Set. All patients in the PP Set will be analyzed by the treatment as randomized. The PP Set will be used for primary efficacy analyses.

4.4. Per-Protocol Analysis Set, Month 6 (PP6)

The Per-Protocol Analysis Set, Month 6 (PP6) will be comprised of all mITT patients who do not have a Grade 4 or Grade 5 protocol deviation impacting Baseline through Month 6 (as per [Section 7](#)). Deviations which end before the Baseline visit date will not impact inclusion in the PP6 Set. All patients in the PP6 Set will be analyzed by the treatment as randomized. The PP6 Set will be used for exploratory efficacy analyses.

4.5. Pre-Randomization Vaseline Application Set

The pre-randomization Vaseline Application Set will include all patients who were applied Vaseline during the Baseline visit, prior to randomization. This set will be used for summaries of any adverse events due to Vaseline application at the Baseline visit.

Vaseline administration is documented by a positive response to the question, ‘*Did the patient apply the ointment over the full lower eyelid length (nasal to temporal)?*’ on the Physician Observation of Drug Application electronic case report form (eCRF), or, for negative responses to that question, a non-zero response to the subsequent question, ‘*If not, to what percentage of the lower lid margin was the ointment applied?*’.

4.6. Safety Set

The Safety Set will include all patients who were administered at least one dose of randomized study medication. Patients will be analyzed according to treatment received. The Safety Set will be used for all analyses of safety data.

5. GENERAL ASPECTS FOR STATISTICAL ANALYSIS

5.1. General Methods

All analyses and summaries will be produced using SAS[®] version 9.4 (or higher). Data will be summarized descriptively by treatment group.

In general, continuous data will be summarized with descriptive statistics (number of patients, mean, standard deviation, median, minimum, and maximum) and will be analyzed using analysis of covariance (ANCOVA) techniques. Categorical variables will be summarized by sample size (N), frequency count, and percent, and will be analyzed using Cochran-Mantel-Haenszel (CMH) to evaluate the difference between treatments, controlling for disease duration category and baseline MGS score category. If CMH comparisons are not estimable, Pearson’s chi-square test or Fisher’s exact test (if the expected cell count is <5 in 25% or more of the cells) will be used.

For analysis purposes, assessments at **unscheduled** visits will be mapped to the nearest scheduled visit (e.g., analysis visit), using the following approach, as summarized in [Table 3](#). All unscheduled visits prior to the Baseline visit date, or in patients who have not had a Baseline visit, will be mapped to the Screening visit.

For assessments scheduled for every study visit: Study visits are scheduled to occur at 14, 42, 84, 126, and 168 days after the Baseline visit for the Day 14, Month 1.5, Month 3, Month 4.5, and Month 6 visits respectively. Therefore, the numbers of days between those visits, not counting the actual visit days, are 13, 27, 41, 41, and 41. Dividing those periods in half and rounding down, the windows around visits should extend to 6, 13, 20, 20, and 20 days after the scheduled visit day. The next window should start the day after the prior window ends, resulting in the following windows:

- Baseline visit date through Baseline visit date + 6: mapped to Baseline visit.
- Baseline visit date + 7 through Baseline visit date + 26: mapped to Day 14 visit.

- Baseline visit date + 27 through Baseline visit date + 61: mapped to Month 1.5 visit.
- Baseline visit date + 62 through Baseline visit date + 103: mapped to Month 3 visit.
- Baseline visit date + 104 through Baseline visit date + 145: mapped to Month 4.5 visit.
- Baseline visit date + 146 or later: mapped to Month 6 visit.

For assessments not scheduled at every study visit: The same approach will be used, omitting the visits without planned assessments from the algorithm. For example, vital signs and Schirmer's assessment are planned for Baseline, Month 3, and Month 6 visits. The numbers of days between those visits are 83 in both cases, resulting in the first 41 days of the period being assigned to the earlier visit. Therefore:

- Baseline visit date through the Baseline visit date + 41 would be assigned to the Baseline visit;
- Baseline visit date + 42 through Baseline visit date + 125 would be assigned to the Month 3 visit, and
- Baseline visit date + 126 or later to the Month 3 visit.

In cases where an assessment is not scheduled to be performed at the Baseline visit, but is scheduled only at the Screening visit, Month 3, and Month 6, (such as IOP, meibography, or ophthalmology), visits prior to and including the Baseline visit will be windowed to the Screening visit, and visits between the Baseline and Month 3 visits will be windowed to Month 3. Visits between Month 3 and Month 6 will be split as described above.

Assessments conducted at the time of **early termination** (defined as assessments performed on the date of early termination or recorded on the same date as an End of Study visit is entered in the subject visit case report form [CRF] page) will also be mapped to the nearest planned visit, as described for unscheduled visits.

Table 3 Mapping of Unscheduled and Early Termination Visits

Visit	Date with Regards to Baseline Visit	Study Day	Analysis Visit Mapping		
			Assessments Performed Each Visit	Assessments Performed at Screening, Baseline, Month 3, and Month 6	Assessments Performed at Screening, Month 3, and Month 6
Screening	Baseline -14 d	-14	Screening	Screening	Screening
Baseline	Baseline	1	Baseline	Baseline	
			
	Baseline + 6 d	7			
	Baseline + 7 d	8			
			
Day 14	Baseline + 14 d	15	Day 14		Month 3

Visit	Date with Regards to Baseline Visit	Study Day	Analysis Visit Mapping		
			Assessments Performed Each Visit	Assessments Performed at Screening, Baseline, Month 3, and Month 6	Assessments Performed at Screening, Month 3, and Month 6
			
	Baseline + 26 d	27			
	Baseline + 27 d	28	Month 1.5		
			
	Baseline + 41 d	42			
Month 1.5	Baseline + 42 d	43			
	Month 3	Month 3	
	Baseline+61 d	62			
	Baseline+62 d	63			
			
Month 3	Baseline + 84 d	85	Month 4.5		
			
	Baseline+103 d	104			
	Baseline+104 d	105			
	Month 6	Month 6	Month 6
	Baseline+125 d	126			
Month 4.5	Baseline+126 d	127			
			
	Baseline+145 d	146	Month 6		
	Baseline+146 d	147			
			
Month 6	Baseline + 168 d	169			
			
	End of Study				

Abbreviations: d = day(s).

Note: Ellipses indicate all dates between the prior and subsequent lines.

If multiple assessments are mapped to the same analysis visit (such as the scheduled visit and 1+ unscheduled visits), the following approach will be used:

- If only 1 non-missing result is present, that result will be used for summaries and analyses.
- If >1 non-missing result is present, the result collected later (chronologically) will be used for summaries and analyses.

All relevant patient data will be included in the listings. All information entered into the database will be included in patient data listings, including data not used for analysis purposes. Data will be listed by the nominal time point collected (whether a scheduled visit or unscheduled visit). Listings will display treatment as randomized. In the event that actual treatment differs from treatment as randomized, a footnote will be added to listings as appropriate, to provide specific information.

Summary statistics will be presented to the degree of precision provided in [Table 4](#).

Table 4 Reporting Precision

Statistics	Degree of Precision
Mean, Median, Quartiles, Confidence intervals	One more decimal place than the raw data
Standard deviation (SD), Standard error (SE)	Two more decimal places than the raw data
Minimum, Maximum	The same number of decimal places as the raw data
p-value	Rounded to 4 decimal places and formatted as 0.xxxx; values smaller than 0.0001 as '<0.0001'
Percent	One decimal place

All fractional numeric values will be presented with a zero to the left of the decimal point (for example, 0.12-0.30, not .12-.30).

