5.2. Key Definitions

5.2.1. Date of First Dose of Study Treatment

The date of first dose of study treatment will be the date of the Baseline visit, at which the randomized study treatment is dispensed. Patients are to be instructed to apply the first dose at home that evening. Patients who do not have confirmation of study treatment administration (defined as non-zero number of doses taken, on a study drug compliance eCRF at the Month 1.5 visit) will not have a date of first dose defined. If a patient takes zero doses before the Month 1.5 visit but does take subsequent doses, the date of first dose will reflect the date of dispensation of the first study treatment applied.

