5.2.2. Baseline Values

The baseline assessment will be the last available measurement taken on or before the date of first dose of study treatment, including any assessments at unscheduled visits. Measurements taken on the date of first dose of study treatment will be considered to be taken prior to first dose. Baseline values are typically collected at the Baseline visit.

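### SAP 5.1 files some post-dose unscheduled and early-exit values under Baseline, contrary to 5.2.2; descriptive Baseline rows and early leavers' post-baseline values are exposed, not the primary result (minor)

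*SAP*

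**What the plan says.** SAP 5.1 (General Methods) and Table 3 map unscheduled assessments to the nearest planned visit, and early-termination assessments follow the same mapping.

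- Assessments made at every visit: "Baseline visit date through Baseline visit date + 6: mapped to Baseline visit".
- Vital signs and Schirmer: "Baseline visit date through the Baseline visit date + 41 would be assigned to the Baseline visit". Days +42 to +125 go to Month 3, and the last line reads "Baseline visit date + 126 or later to the Month 3 visit".
- IOP, meibography and ophthalmoscopy, which have no Baseline-visit assessment: "visits between the Baseline and Month 3 visits will be windowed to Month 3".
- Several results at one visit: "If >1 non-missing result is present, the result collected later (chronologically) will be used for summaries and analyses".

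SAP 5.2.1 sets the first-dose date at the Baseline visit: "Patients are to be instructed to apply the first dose at home that evening". SAP 5.2.2 then defines baseline: "The baseline assessment will be the last available measurement taken on or before the date of first dose of study treatment", and it expressly includes unscheduled visits. SAP 5.3, on missing efficacy data, lists only Day 14, Month 1.5, Month 3, Month 4.5 and Month 6 as mapping targets, and its own example sends an exit at Day 40 to Month 1.5. SAP 10.6 summarizes vital signs as absolute values by time point. The protocol synopsis (Visit Schedule) asks Expansion Cohort patients who leave early to complete the Month 6 procedures, which by SAP Table 2 include vital signs and Schirmer.

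**The concern.** A value taken after the first dose is a treated value. If 5.1 is followed literally, such a value is filed under Baseline and, being later, displaces the pre-dose value there. Two outputs suffer.

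First, the rows labelled Baseline can mix untreated and treated values. This matters most for vital signs, where no change score is planned that would show the discrepancy. It also affects the actual-value summaries of Schirmer, an exploratory endpoint. These rows need not agree with the baseline that 5.2.2 uses to compute change.

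Second, a patient who leaves by +41 and has vital signs and Schirmer measured at exit contributes no post-baseline value of either to the summaries. The values survive only in listings. Early leavers are a group whose on-treatment safety values one would want to see.

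There is also an ambiguity for programmers. An MGYLS or OSDI value on Day +3 is Baseline under 5.1 and Day 14 under 5.3, and it is not carried forward under 5.3.2, which starts at Day 14.

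**Working it through.** **Reproducing the windows.** The rule in 5.1 is: window end = visit day + half the days strictly between visits, rounded down. The visit days are 0, 14, 42, 84, 126 and 168.

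- Every-visit assessments: 14 - 0 - 1 = 13 days between; 13/2 rounds down to 6; window end +6. This matches.
- Vital signs and Schirmer: 84 - 0 - 1 = 83; 83/2 rounds down to 41; window end +41. This matches.
- The same measures after Month 3: 168 - 84 - 1 = 83; 84 + 41 = 125. This matches, so +126 onward belongs to Month 6, as Table 3 shows. The bullet naming Month 3 is an error.

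**Treatment inside the windows.** SAP 10.1 gives expected doses as 2 x (end - start + 1)/7.

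- By +6: 2 x 7/7 = 2 doses.
- By +41: 2 x 42/7 = 12 doses.

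**Side by side.**

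- Schirmer at an exit on +40: Baseline under 5.1; Month 1.5 under 5.3; not baseline under 5.2.2.
- OSDI on +3: Baseline under 5.1; Day 14 under 5.3; not baseline under 5.2.2.
- Vital signs on +40: Baseline under 5.1; not baseline under 5.2.2. Section 5.3 does not apply, because it concerns efficacy data.

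**How many patients.** The documents give no dropout rate. Assume that 5-15% of 225 leave by Month 3 (11.25 to 33.75 patients), evenly over 84 days.

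- Exits on Days 1-41: 11.25 x 41/84 = 5.5 and 33.75 x 41/84 = 16.5, so about 5-16 (1.8-5.5 per arm).
- Protocol 7.2 allows exit procedures to wait for the next scheduled visit. If all wait, exits on Days 1-14 are assessed at about +14: 11.25 x 14/84 = 1.9 and 33.75 x 14/84 = 5.6, so about 2-6. To these add any later leaver whose Month 1.5 visit falls at +35 to +41, which its window of 42 plus or minus 7 days allows.
- Unscheduled visits would add to either figure, and the documents give no basis for counting them.

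**Bound for the primary measures.** Exits on Days 1-6: 11.25 x 6/84 = 0.80 and 33.75 x 6/84 = 2.41 in all, or 0.27-0.80 per arm. Suppose each had already moved by the full 0.5% planning mean in SAP Table 1 (2.77 glands; 8.36 OSDI points). The arm's Baseline row would shift by 0.27/75 x 2.77 = 0.01 to 0.80/75 x 2.77 = 0.03 glands, and by 0.27/75 x 8.36 = 0.03 to 0.80/75 x 8.36 = 0.09 OSDI points. Against the planned difference of 2.0 glands that is 0.5-1.5%. It is a shift in a descriptive row, not in the tested difference. It counts exits only.

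**The case against.** The best reply is that 5.2.2 already settles the matter. It is the specific definition of baseline, it names unscheduled visits, and it can be read as the exception to the later-value rule. That largely stands: where a first-dose date is defined, the ANCOVA covariate and the change scores are protected. What 5.2.2 does not clearly settle is which value fills a summary row labelled Baseline, and the table shells that might do so are in a separate document. The exposed outputs are descriptive or exploratory, which limits the weight of the point.

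A reader might infer three stronger things that the documents do not support.

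- *That the primary analysis is biased through the imputation variable Day1.* SAP 5.3.1.1 does invoke the 5.1 mapping and later-value rule, but 5.3 excludes Baseline as a target and 5.2.2 ends baseline at first dose. This is an ambiguity to close, not a shown bias.
- *That 5.2.2 fails for the very patients concerned.* SAP 5.2.1 says that those without confirmed dosing "on a study drug compliance eCRF at the Month 1.5 visit) will not have a date of first dose defined". Read literally, someone who leaves before Month 1.5 could lack that date. The eCRF design is not shown, so this is a wording risk only.
- *That the IOP rule shows the authors saw the problem and that it should simply be extended to Schirmer.* The IOP rule exists because IOP is not measured at the Baseline visit. Extending it to Schirmer would enter a Day 2 exit value as observed Month 3 data in the ANCOVA and responder analyses of SAP 8.3.1. That amounts to carrying it forward where most efficacy analyses use multiple imputation, and it would still conflict with the Day 40 example in 5.3.

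**Conclusion.** The conflict in the text is real. SAP 5.1 and Table 3 place post-dose values under Baseline, contrary to 5.2.2 for all assessments and contrary to 5.3 for efficacy assessments, Schirmer included. The consequence is limited to descriptive Baseline rows, chiefly vital signs and Schirmer, and to the loss of values taken by +41 from the post-baseline summaries of those two measures. The effect on the primary result is negligible. The patient counts rest wholly on the assumed 5-15% dropout and even timing, and they are not a ceiling because unscheduled visits are uncounted. The +126 line is a plain error that Table 3 and the stated algorithm resolve. Severity: minor.

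**What to change.** - State in 5.1 and Table 3 that 5.2.2 governs the Baseline visit everywhere, including Day1 in the imputation. No value dated after first dose, or after the Baseline visit date if no first-dose date is defined, may enter the Baseline window.
- Vital signs: assign post-dose values that precede the Month 3 window to a post-baseline row, for example Month 3 as for IOP. Say explicitly that a scheduled Month 3 value takes precedence, because the later-value rule alone would not ensure this for an unscheduled value taken between that visit and +125.
- Schirmer: show values from +1 to +41 in listings only, do not use them as observed Month 3 data, and amend 5.3 to agree.
- Every-visit efficacy values on Days +1 to +6: listings only. This leaves the Day 14 limit in 5.3.2 unchanged; amend 5.3 to agree.
- Change the destination of +126 or later to Month 6.

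The cost is wording in 5.1, Table 3 and 5.3 and a small programming change, with no extra data or patients. The downside is that a few very early values appear only in listings or under a later safety visit label.
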